5.3.6 Diversity and inclusion questionnaire

A diversity and inclusion questionnaire will be completed at baseline. This self- administered questionnaire asks about age, disability, ethnic background, gender, religion and socioeconomic background. The results will be summarised descriptively and the diversity and inclusion of the study will be reported for each category and group (CMT/ PiP).

5.3.7 Musculoskeletal Patient Reported Experience Measure

A patient reported experience measure will be completed at 14 weeks. This self- administered questionnaire asks about patient's experiences of undergoing an intervention for their condition. Questions 1-12 focus on satisfaction, being involved in decisions, feeling listened

to, explanations, time, care, confidence, review opportunities, information, care coordination, needs, guidance. Questions 1-12 have 3 levels of responses for each domain (3= yes, definitely, 2= yes to some extent, 1= no not at all. Question 13 has five levels of responses for each domain (5= extremely, 4= very, 3= moderately, 2= slightly, 1= not at all. Question 14 has five levels of responses (5= very good, 4= good, 3= neither good nor poor, 2= very poor, 1= don't know.

Follow-up

Participants in both arms will complete all secondary outcomes at baseline, 14 weeks and 6 months post-randomisation.

6. Data

7.1 Electronic/non-paper data

The secondary outcome measures described in section 5.2 have been set up on JISC (web-based digital resource for online surveys. Participants are sent an email from JISC which includes links to each of the outcomes. The participants will complete the outcome measure questionnaires online at baseline, 14 weeks and 6 months post-randomisation. The results are stored on JISC until analysis.

7.2 External datasets

1. Recruitment data will be stored in a recruitment screening log and spreadsheet by the trial research coordinator.
2. Consent data will be stored in a consent log and spreadsheet managed by the trial research coordinator.

7. Sample Size

We plan to recruit 48 participants to the study. Assuming a dropout of 20%, this should provide approximately 19 in each group for the final analysis. The primary objective of this study is to assess the feasibility, and inform planning, of a future large-scale clinical trial. Sample sizes of between 24 and 70 have been recommended for feasibility trials to provide a reliable estimate of parameters required to calculate the sample size for a main trial, e.g. standard deviation of continuous outcomes, recruitment, and attrition rates. Our sample of 48 is therefore in line with these recommendations.

8. Randomisation

Randomisation will be carried out via a web-based randomisation system (<https://www.sealedenvelope.com/>). The allocation sequence will be generated by the lead or co-investigator not otherwise involved in the recruitment/treatment of participants. Once group allocation has been confirmed the intervention coordinator (member of the research team) will liaise with participants over the phone to schedule the appointments.

10. Analysis

10.1 Analysis software

Analyses will be mainly conducted in SPSS Statistics 28, whereas health economic analysis will be conducted in Stata (version 15 or later; Stata Corp LLC; College Station, TX).

10.2 Baseline data

Baseline data (demographics and outcome measures collected post-randomisation) will be summarised descriptively by treatment and control group both as randomised, and for participants followed up at 6 months. Continuous variables will be summarised using mean and standard deviation (SD), and number and percentage for categorical. A template of the table used to present baseline characteristics can be viewed in Appendix A. No formal statistical comparisons will be undertaken on baseline data.

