This analysis plan was written prior to the completion of recruitment and was prepared according to UoS SOPs and guidance documents.

2. Definition of terms/acronyms

AE	Adverse event
CONSORT	Consolidated standards of reporting trials
CMT	Cognitive muscular therapy
NIHR	National Institute of Health Research
CTIMP	Clinical trial of Investigational Medicinal Product
RCT	Randomised controlled trial.
SAE	Serious adverse event
SAP	Statistical analysis plan

3. Design

This study is an open, multi-centred, two-armed feasibility, randomised trial with allocation at the patient level, with embedded health economic and qualitative evaluations (not detailed further in this SAP). The two arms are: cognitive muscular therapy (CMT) and psychologically informed physiotherapy

Full details of the background and design of the trial are presented in the protocol (Protocol-(COMPIN)- v5 (17-04-24).docx)

4. Trial objectives

This trial aims to deliver key parameters that are required to run a future, pragmatic, two-arm RCT.

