10.4 Outcome data

Outcome data will be summarised descriptively by group (treatment vs control) and timepoint. We will plot line graphs to look at the trajectory of each outcome over time, looking at both individual participants and the mean values for each randomised group. As this is a feasibility study, no formal hypothesis testing will be undertaken to compare outcomes between the groups. Templates of the tables used to present outcome data can be viewed in Appendix (C). Potential clinical effectiveness will be considered by investigating the number of participants who experience a 30% improvement in pain/ function as measured by the Neck Disability Index at 6 months. We will also calculate the mean difference in the NDI score between the intervention and control groups, with a one-sided 80% and 90% confidence interval (CI) for this difference to see whether the interval includes the kind of difference that we would be looking for in the main trial. If, for instance, we saw a negative point estimate and our CI excluded say a 0.3 SD difference then this would be suggestive that it may not be worth moving forward to the main trial - at least with the intervention as tested in the feasibility study.

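### SAP section 10.2 places the baseline outcome measures after randomisation in an open trial, which exposes the baseline-dependent summaries to knowledge of allocation

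*SAP*

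**What the plan says.** Section 10.2 fixes the timing of baseline: "Baseline data (demographics and outcome measures collected post-randomisation) will be summarised descriptively". Section 3 describes the design: "This study is an open, multi-centred, two-armed feasibility, randomised trial with allocation at the patient level".

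Section 7.1 gives the mode of collection: "The participants will complete the outcome measure questionnaires online at baseline, 14 weeks and 6 months post-randomisation". Section 5.2.1 describes the NDI as a self-report instrument scored 0 to 50.

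Section 8 describes what follows allocation: "Once group allocation has been confirmed the intervention coordinator (member of the research team) will liaise with participants over the phone to schedule the appointments". It does not say whether the baseline survey comes before or after that call.

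Four parts of the plan use baseline scores:

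- Section 10.4 counts "the number of participants who experience a 30% improvement in pain/ function as measured by the Neck Disability Index at 6 months". It names no reference value, but improvement needs one and baseline is the only plausible candidate.
- Section 10.4 plots each outcome over time, by participant and by group mean.
- Section 10.8 builds QALYs by the trapezoidal method from EQ-5D-5L at baseline, 14 weeks and 6 months.
- Section 10.2 and Appendix A tabulate baseline outcome scores by arm.

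**The concern.** A baseline is useful because it cannot depend on the allocation. If a participant already knows the arm, relief, expectation or disappointment can move the answers to questions about pain, disability, catastrophising and fear of movement. Willingness to complete the survey can also differ by arm. Section 10.5 gives the arms different numbers of sessions (7 for CMT, 5 for PiP), so a scheduling conversation could reveal the allocation in an open trial.

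A shift in one arm's recorded baseline then looks like a difference in improvement even if the arms do equally well, and later analysis cannot recover the uncontaminated value. The trial is also meant to settle procedures for a larger RCT, so the sequence could be carried forward. The SAP was written before recruitment ended, so the order could still be put right for any participants not yet randomised.

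**Working it through.** **The plan's own figure.** Section 7 expects 48 recruits and 20% dropout: 48 × (1 − 0.20) / 2 = 19.2 per group, which matches the stated 19. The timing of baseline does not change this.

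**Does any other text override section 10.2?** The Follow-up paragraph after section 5.3.7, and section 7.1, list baseline with the two follow-up times and the qualifier post-randomisation. Neither places baseline before randomisation. Nothing in the SAP makes randomisation wait for a submitted baseline survey. Section 10.2 is therefore the only explicit statement of timing.

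**One patient.** Improvement = (baseline − follow-up) / baseline.

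- Recorded 15, then 11: 4/15 = 26.7%, not a responder.
- Recorded 16, then 11: 5/16 = 31.25%, a responder.

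One point on a 50-point scale changes the classification.

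**One arm.** The SAP gives no NDI mean, SD or correlation, so all of these are assumptions: baseline mean 12, 16 or 20; SD 5 or 7; correlation between baseline and 6 months 0.5 or 0.7; mean fall of 20% in both arms, so no true difference. Follow-up score = 0.8 × mean + correlation × (baseline − mean) + SD × √(1 − correlation²) × standard normal error. Scores were rounded and kept within 0 to 50. The recorded baseline in one arm was then raised by a fixed number of points, with 400,000 simulated patients per setting. With no shift, the responder share ran from 29% to 44% across the twelve settings.

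| Shift in recorded baseline | Rise in responder share | Extra responders in an arm of 19 |
|---|---|---|
| 1 point | 4.0 to 7.8 percentage points | 0.8 to 1.5 |
| 2 points | 8.6 to 15.5 | 1.6 to 2.9 |
| 3 points | 13.1 to 23.1 | 2.5 to 4.4 |

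The last column is the rise × 19. A downward shift would act in the opposite direction.

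**QALYs.** Taking 6 months as 26 weeks, the trapezoidal area is 14 × (u0 + u14)/2 + 12 × (u14 + u26)/2 = 7·u0 + 13·u14 + 6·u26. Baseline utility carries 7/26 = 27% of the weight.

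**What does not move.** An unadjusted difference in 6-month NDI scores contains no baseline term. The quantitative stop-go criteria in section 4.2 concern recruitment, session attendance and data provision; acceptability is judged qualitatively. None uses a baseline clinical score. Age, gender, ethnicity and occupation are hardly open to expectation effects.

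**The case against.** **It may be a drafting slip.** The SAP has other stray text: 8 months in section 10.5 and the Appendix A title against 6 months elsewhere, and a WOMAC row in the Appendix C outcome table of a neck-pain trial. In section 7.1 the qualifier post-randomisation reads naturally as belonging to the follow-ups only. This stands as a possibility, and the document cannot settle it. It does not remove the point, because section 10.2 then misstates when baseline was measured and still needs correcting.

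**Knowledge of allocation at baseline is not shown.** A reader might infer that participants do know their arm when they answer. The SAP does not say so. The call in section 8 is for scheduling and is not ordered against the survey, and the protocol may give the sequence. This stands: contamination is possible on the text, not established. But the SAP has not left timing to the protocol; it states a timing, and that timing permits the problem.

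**The 0.3 SD margin.** A reader might infer that the bias eats into the 0.3 SD difference in section 10.4. With an assumed 0.2 SD baseline shift, a change-score difference would be off by 0.2 SD, and a baseline-adjusted one by 0.5 × 0.2 = 0.10 to 0.7 × 0.2 = 0.14 SD. Section 10.4 specifies neither analysis. It asks for a mean difference in NDI score, and on unadjusted 6-month scores the bias from this source is zero. No bias relative to that margin should be claimed.

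**The consequences are limited.** There is no primary clinical outcome and no formal hypothesis test. Section 10.3 already logs collected and analysable baseline data by arm, so unequal baseline completion would be visible. All of this stands and confines the point to the descriptive quantities listed.

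**Conclusion.** The point holds in a limited form. As written, section 10.2 lets self-reported baseline scores be collected after a participant may have learned the allocation. This can bias the 30% NDI responder count, the trajectories, the QALY area under the curve and the self-reported outcome rows of the baseline table.

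The illustrated size is about 1 to 4 responders in an arm of 19, for a shift of 1 to 3 NDI points in one arm. It rests on baseline being the reference for the 30% improvement, on the assumed NDI distribution, and on a shift whose existence, direction and size the SAP does not establish.

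It would go too far to say that the baseline table can no longer show whether the arms are comparable, since its demographic rows remain informative. It would also go too far to say that the progression decision is compromised through the stop-go criteria.

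**What to change.** In section 10.2, state that baseline questionnaires are completed after consent and before randomisation, or at the least before allocation is disclosed, and that randomisation is released only once the baseline survey is submitted. If post-randomisation is a slip for pre-randomisation, correct the word.

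For participants already randomised, use the available survey and randomisation timestamps to report, by arm, how many baselines were completed after randomisation. Where the time of disclosure is recorded, count against that too, since a randomisation timestamp need not capture it. Present the 30% NDI responder count with that caveat.

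A summary without late baselines should be no more than a labelled sensitivity analysis. If section 10.2 is literally true it would exclude everyone. If only some baselines are late, it selects participants on a post-randomisation event and breaks the randomised comparison in groups of about 19.

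The cost is a wording change, a small data check and possibly a short delay between consent and randomisation. The sample size is unchanged.

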10.3 Screening, eligibility, recruitment and follow-up data

A CONSORT diagram will be produced to detail participant flow through the trial (Appendix B). A recruitment, screening and consent log will be kept detailing participation in the study. This data will be used to determine:

- Numbers screened and sent PIS by clinical research nurse per research site.
- Proportion of participants screened who contacted the research coordinator per site.
- Proportion of participants who were eligible per research site.
- Proportion of participants consented per research site.
- Proportion of participants withdrawn per research site.

Recruitment graphs presenting the overall recruitment per month and the actual vs target recruitment will be produced.

The type and timing of withdrawals will be presented overall and by randomised group, with reasons where available. Templates of the tables used to present recruitment and retention data can be viewed in Appendix (C).

A log detailing the proportion of collected and analysable outcome data per follow up timepoint will be kept. This log will include:

- Baseline data for each arm and all outcome measures.
- 14-week data for each arm and all outcome measures.
- 6-month data for each arm and all outcome measures.

10.4 Outcome data

Outcome data will be summarised descriptively by group (treatment vs control) and timepoint. We will plot line graphs to look at the trajectory of each outcome over time, looking at both individual participants and the mean values for each randomised group. As this is a feasibility study, no formal hypothesis testing will be undertaken to compare outcomes between the groups. Templates of the tables used to present outcome data can be viewed in Appendix (C). Potential clinical effectiveness will be considered by investigating the number of participants who experience a 30% improvement in pain/ function as measured by the Neck Disability Index at 6 months. We will also calculate the mean difference in the NDI score between the intervention and control groups, with a one-sided 80% and 90% confidence interval (CI) for this difference to see whether the interval includes the kind of difference that we would be looking for in the main trial. If, for instance, we saw a negative point estimate and our CI excluded say a 0.3 SD difference then this would be suggestive that it may not be worth moving forward to the main trial - at least with the intervention as tested in the feasibility study.

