4.1 Primary objective

This trial aims to gain insight into whether CMT is more effective than PiP for patients with chronic non-specific neck pain.

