5.1 Primary outcome(s)

This research is a feasibility trial and therefore does not have a primary clinical outcome measure. The primary outcomes will therefore relate to the feasibility of conducting a future, fully powered RCT (recruitment, retention, and intervention adherence rates) and obtaining parameters required to inform its design and conduct, such as the standard deviation of outcome measures that may feed into the sample size calculation.

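### SAP 10.4 names no baseline adjustment for the NDI difference, so a valid interval is wider than it need be and exposed to chance imbalance

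*SAP*

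**What the plan says.** **The estimate.** SAP 10.4: "We will also calculate the mean difference in the NDI score between the intervention and control groups". The same sentence specifies the uncertainty to be shown: "with a one-sided 80% and 90% confidence interval (CI) for this difference". No model, covariate or change score is named. The sentence gives neither the time point nor the SD that defines the reference difference.

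**Its use.** If the estimate were negative and "our CI excluded say a 0.3 SD difference", the conclusion the SAP would draw is that "this would be suggestive that it may not be worth moving forward to the main trial". The wording is by way of example.

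**Baseline data.** Under Follow-up, after 5.3.7: "Participants in both arms will complete all secondary outcomes at baseline, 14 weeks and 6 months post-randomisation". The NDI is the first secondary outcome in 5.2. Section 10.2 plans only a descriptive summary of baseline values, and describes the baseline outcome measures as gathered after randomisation. Section 3 describes the trial as open.

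**Design parameters.** Section 5.1 wants quantities for planning the main trial, "such as the standard deviation of outcome measures that may feed into the sample size calculation".

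**Objectives.** Section 4.1, the primary objective: "This trial aims to gain insight into whether CMT is more effective than PiP". Section 7: "The primary objective of this study is to assess the feasibility".

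**The concern.** In a comparison of about 19 per arm, the width of the interval determines what it can say about 0.3 SD. A baseline score on the same scale usually predicts the follow-up score. Leaving it out gives up precision on data the trial already plans to collect, and lets a chance difference between arms at baseline carry through into the estimate.

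The adjusted model would also supply the residual SD and the baseline to follow-up correlation. A main trial that adjusts for baseline would need both for its sample size, and the SAP plans to report neither.

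A related inconsistency affects how the estimate is read. If effectiveness is the primary objective, as in 4.1, the NDI difference is the main result. If feasibility is, as in 5.1 and section 7, it is exploratory.

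**Working it through.** **Inputs.** From SAP section 7: 48 recruited, 20% dropout, about 19 per group. From 10.4: one-sided 80% and 90% levels, and a reference of 0.3 SD. Assumed: equal within-arm SD, and a baseline to 6-month NDI correlation r of 0.3, 0.5 or 0.7. Effects are in SD units. Positive means benefit from CMT, which is how the negative estimate in 10.4 appears to be meant.

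**The plan's own figure.** 48 × (1 − 0.20) / 2 = 19.2, so about 19 per group is reproduced.

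**Raw difference.** SE = √(2/19) = 0.324 SD. The margin is t(36 df) × SE:
- 80%: 0.852 × 0.324 = 0.276 SD
- 90%: 1.306 × 0.324 = 0.424 SD

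**Adjusted for baseline NDI.** SE = 0.324 × √(1 − r²) × √(1 + 1/34). The last factor allows for the expected baseline imbalance. The margin uses t on 35 df.

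| r | SE | 80% margin | 90% margin | 90% margin narrower by |
|---|---|---|---|---|
| raw | 0.324 | 0.276 | 0.424 | – |
| 0.3 | 0.314 | 0.268 | 0.410 | 3% |
| 0.5 | 0.285 | 0.243 | 0.372 | 12% |
| 0.7 | 0.235 | 0.200 | 0.307 | 28% |

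A simulation of 20,000 trials gave adjusted SEs of 0.286 at r = 0.5 and 0.235 at r = 0.7, in agreement. The squared ratio of 90% margins gives the equivalent gain in sample size: (0.424/0.410)², (0.424/0.372)² and (0.424/0.307)² are about 1.1, 1.3 and 1.9. Adjustment narrows the interval once r² exceeds 1/35, that is, r above about 0.17.

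**Reading against 0.3 SD.**
- At 80%, every margin is below 0.3. Any negative estimate therefore excludes 0.3 SD, raw or adjusted.
- At 90%, the estimate must be at or below 0.3 − 0.424 = −0.124 SD raw, against −0.110, −0.072 or −0.007 SD adjusted.
- If the true benefit is 0.3 SD, the chance of a negative estimate whose 80% interval excludes 0.3 SD is 17.8% raw, against 17.0%, 14.6% or 10.1%. The corresponding chance at 90% is 9.6% in every case.
- If the true effect is zero, the chance that the 90% reading is discouraging is 35% raw, against 36%, 40% or 49%.

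**Chance imbalance.** The difference in mean baseline NDI between the 19 and 19 analysed has SD √(2/19) = 0.324 SD. The probability that it exceeds 0.3 SD in either direction is 0.36. An imbalance of one SE moves the raw estimate by r × 0.324 = 0.10, 0.16 or 0.23 SD.

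**Objectives.** Section 4.1 puts comparative effectiveness first, and 4.2 lists recruitment and retention as secondary. Section 5.1 says that the trial has no primary clinical outcome and that its primary outcomes concern feasibility. Section 7 says the same of the primary objective. These statements cannot all stand.

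**The case against.** The strongest reply is that nothing here is invalid. In a randomised comparison the raw difference is unbiased, and its interval keeps nominal coverage over repeated randomisations. Section 10.4 is descriptive, and the SAP never says the difference is unadjusted; that is inferred from the absence of any covariate. All of this stands. The fault is lost precision, and sensitivity of the estimate to whatever imbalance occurs.

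Several stronger readings are tempting, and the SAP does not support them:
- **That 0.3 SD is a decision rule.** The wording in 10.4 is illustrative, and the stop-go criteria in 4.2 contain no NDI interval.
- **That the gain is certain to be large.** It depends on a correlation the SAP does not give. At r = 0.3 it is about 3%.
- **That every participant will have a baseline NDI.** It is scheduled, but 7.1 has it completed online from an emailed link, and 10.3 treats the completeness of baseline data as something to be logged.
- **That the main trial could not otherwise be sized.** It could be sized on the outcome SD, which 5.1 intends to obtain, and the correlation could be computed later from the stored data.
- **That low power condemns 4.1.** The SAP plans no hypothesis test, and 4.1 speaks only of gaining insight. The problem in 4.1 is its conflict with 5.1 and section 7.

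One objection bears on the remedy. If baseline NDI really is completed after randomisation in an open trial, some scores may be reported with allocation known, and adjusting for them could introduce bias. This must be settled before the adjusted estimate takes the lead. The statement that formal testing is not planned is no obstacle, because an adjusted estimate with an interval is not a test.

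**Conclusion.** The point holds as a worthwhile improvement in precision, not as the correction of an invalid analysis. The 90% margin of 0.424 SD would fall by 3%, 12% or 28% at an assumed correlation of 0.3, 0.5 or 0.7. The 80% margin also narrows, but at that level a negative estimate excludes 0.3 SD either way. The figures rest on 19 per arm, a common SD, and a baseline score not influenced by knowledge of allocation. The conflict between 4.1 and 5.1 with section 7 is a separate matter of wording and rests on no assumption.

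**What to change.** - **Section 10.4.** Estimate CMT minus PiP in NDI at 6 months from a linear model with arm and baseline NDI. Base the one-sided 80% and 90% intervals on it and show the raw difference alongside. State which SD defines 0.3 SD. State the direction too: higher NDI is worse, so benefit from CMT is a negative difference on this scale.
- **Design parameters.** Report the pooled within-arm SD, the residual SD and the baseline to 6-month correlation.
- **Section 10.2.** Correct or clarify when baseline outcomes are completed. Adjust using baseline NDI completed before allocation is known. If some were completed afterwards, report how many and keep the raw difference as a sensitivity analysis. Say how participants without a usable baseline score are handled, and report their number.
- **Section 4.** Make feasibility the primary objective and insight into effectiveness exploratory, in line with 5.1 and section 7.

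The cost is one regression in SPSS, already the named software, one degree of freedom, and wording changes. If 10.2 is literally true, the order of collection can change only for participants not yet enrolled, which is why the sensitivity analysis is needed.

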patients that are reimbursed by NHS will be considered. Health care utilisation data at each follow-up time point will be collected and presented for relevant resources used by patients in primary care, community (i.e. appointments with a GP, nurse, physiotherapist, occupational therapist, and other primary/community care healthcare professionals) and hospital setting (i.e. hospital outpatient attendances, accident and emergency admissions, day case attendances and inpatient admissions). Participants will be asked to record their resource use specifically in relation to neck pain and whether the appointment/contact was face-to-face or remote (phone/online). Mean resource use by cost category will be summarised, and completion rates will be presented. Considering that this is a feasibility trial and full economic evaluation was deemed unnecessary, unit costs for the healthcare resources will not be attached to the units of resource utilisations to derive the total costs.

Missing EQ-5D-5L and resource utilisation data will be inspected to understand the likely mechanism of missingness to help guide appropriate imputation methods to deal with the missing data.

As full economic evaluation is not necessary, the common issues around trial-based economic evaluation such as baseline imbalances, correlated costs and effects, and skewness of costs and effects will not be considered in our study. The sampling uncertainty will not be considered as well and as a result, non-parametric bootstrapping will also not be applied.

9. SAP amendment log

Amendment/addition to SAP and reason for change	New version number, name and date
Draft	V1.0
Draft	V2.0
Signed version	V3.0

10. Signatures of approval

Sign-off of the final approved version of the Statistical Analysis Plan by the principle investigator and trial statistician(s) (can also include Trial Manager/Co-ordinator)

Name	Trial Role	Signature	Date

11. References

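### Section 10.4 takes a plain difference in NDI means, by implication on completers; using baseline and 14-week NDI would cut its SE and limit bias from loss that differs by arm

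*SAP*

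**What the plan says.** - **Estimate.** Section 10.4: "We will also calculate the mean difference in the NDI score between the intervention and control groups". It attaches two one-sided limits, at 80% and at 90%. It names no time point for the difference, no covariate and no analysis set. The sentence before it counts participants with a 30% NDI improvement at 6 months, without a denominator.
- **Use.** The same section gives an example of how the result would be read: "If, for instance, we saw a negative point estimate and our CI excluded say a 0.3 SD difference", this would suggest that the main trial may not be worth pursuing.
- **Numbers.** Section 7 (Sample Size): "We plan to recruit 48 participants to the study" and "Assuming a dropout of 20%, this should provide approximately 19 in each group for the final analysis".
- **Data collected.** The Follow-up paragraph before section 6: "Participants in both arms will complete all secondary outcomes at baseline, 14 weeks and 6 months post-randomisation". The NDI is one of these outcomes.
- **Plots.** Section 10.4 plans line graphs over time, "looking at both individual participants and the mean values for each randomised group".
- **Missing data.** Sections 5.2.2 and 5.2.3 have item-level rules for the PCS and the Tampa scale. Section 10.8 adds: "Missing EQ-5D-5L and resource utilisation data will be inspected to understand the likely mechanism of missingness". None of these covers the NDI.
- **Appendix C.** The outcome table is headed for N, mean and SD at each follow-up visit, but it has no NDI row.

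**The concern.** The NDI difference is the only between-arm effect estimate with an interval in the plan. Section 4.1 makes insight into comparative effectiveness the primary objective, and section 10.4 links this interval to the question of a main trial. As described, the estimate is a subtraction of two observed means. It does not use baseline NDI, which every participant is due to provide, or the 14-week NDI of people who do not answer at 6 months.

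Two things follow. The estimate is less precise than the collected data allow. And if people doing badly at 14 weeks are less likely to answer at 6 months in one arm than in the other, part of the observed difference comes from who stayed. Such a difference in loss is conceivable here: the trial is open, outcomes are self-completed online, and full attendance means 7 sessions in one arm and 5 in the other (section 10.5). The plotted arm means and the responder count have the same weakness.

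**Working it through.** **Inputs from the SAP.** 48 recruited, 20% dropout, about 19 per group analysed (equal allocation is implied), one-sided 80% and 90% limits, and 0.3 SD as the example value.

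**Assumed inputs (not in the SAP).** The gap in 6-month NDI between completers and dropouts. For the simulation: 24 per arm, 5 lost per arm after 14 weeks, correlations of 0.5 (baseline with each follow-up) and 0.7 (14 weeks with 6 months), and no true effect.

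**1. The plan's own figure.** 48 × 0.80 / 2 = 19.2 per arm, which reproduces the stated 19. The figure therefore fits an analysis of those with data.

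**2. Precision of the raw difference.** SE = SD × √(2/19) = 0.324 SD. With a baseline correlation of 0.5, adjustment multiplies this by √(1 − 0.5²) = 0.866, giving 0.281 SD.

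**3. Bias from loss.** With dropout fractions d1 and d2, and gaps g1 and g2 (completer mean minus dropout mean, in SD), bias = d1 × g1 − d2 × g2. At 20% in both arms:

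| Pattern of loss | Gap (SD) | Bias (SD) |
|---|---|---|
| Same gap in both arms | any | 0 |
| One arm only | 0.5 / 1.0 / 1.5 | 0.10 / 0.20 / 0.30 |
| Opposite directions | 0.25 / 0.5 / 0.75 | 0.10 / 0.20 / 0.30 |

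Unequal dropout of 10% and 30% with a common gap of 0.5 or 1.0 SD gives 0.20 × gap = 0.10 or 0.20 SD.

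**4. Ceiling for one-arm selection.** If exactly the worst 20% of one arm on 6-month NDI were lost, the shift would be φ(0.842)/0.80 = 0.35 SD. If selection acts through 14-week NDI, which correlates 0.7 with 6-month NDI, the ceiling is about 0.7 × 0.35 = 0.245 SD.

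**5. Simulation (6000 trials, assumed inputs above).** In the selective case, loss in one arm is weighted to worse 14-week NDI. A weight rising about 4.5-fold per SD reproduces these figures.

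| | Raw difference | Baseline-adjusted completers | Baseline and 14-week NDI |
|---|---|---|---|
| SE, random loss (SD) | 0.321 | 0.281 | 0.270 |
| Bias, one-arm selective loss (SD) | −0.175 | −0.117 | 0.000 |
| SE, one-arm selective loss (SD) | 0.326 | 0.288 | 0.282 |

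A negative bias makes the selected arm look better than it is. Log-weights of 0.5 to 2 per SD gave raw bias of −0.09 to −0.20 SD. The last column uses a regression prediction as a stand-in for the mixed model. The likelihood form of the mixed model agreed: SE from 0.33 to 0.28 SD under random loss, and bias from about −0.17 to 0.00 SD. If no dropout has a 14-week score, about −0.12 SD remains.

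**6. Effect on the example reading.** Take the difference as benefit, positive in favour of CMT; a stop reading needs an estimate below 0 and an upper limit below 0.3 SD. On 36 degrees of freedom the limit lies 0.28 SD (80%) or 0.42 SD (90%) above the estimate. With a true benefit of 0.3 SD:

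| Bias against CMT (SD) | Stop reading, 80% limit | Stop reading, 90% limit |
|---|---|---|
| 0 | 18% | 10% |
| 0.1 | 27% | 16% |
| 0.2 | 38% | 25% |

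**7. Responders.** Assume a true rate of 40%, that is 9.6 of 24. If all 5 lost are non-responders, the rate among those observed is 9.6/19 = 51%. If all 5 are responders, it is 4.6/19 = 24%.

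**The case against.** The case against is substantial.

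- **Stronger readings that a reader might infer.** One is that the expected 20% dropout could by itself produce an apparent effect near 0.3 SD. It cannot: random loss gives no bias, equal selection cancels, and selection through 14-week NDI in one arm stays below 0.25 SD under the assumed correlations. Another is that 0.3 SD is a decision threshold. The wording of 10.4 offers it as an example, the stop-go criteria in 4.2 contain no NDI value, and the example also needs a negative estimate. This stands in full.
- **Completer-only analysis is not stated.** It is inferred from the 19 per group and from silence in 10.4. The 6-month time point is likewise inferred from the preceding sentence. This stands.
- **The plan does address missing data and attrition elsewhere.** Besides the provision in 10.8 there are the PCS and Tampa item rules. Section 10.2 shows baseline data for those followed up, 10.3 gives type, timing and reasons of withdrawal by arm, and 10.5 gives attrition by arm with a 95% CI. These would expose differential loss, but they do not correct the estimate.
- **The benefit of 14-week data is partly built into the simulation.** Loss was made to depend on 14-week NDI, and every dropout had that score. If loss depends on 6-month NDI itself, about −0.13 SD remains. Under random loss, 14-week data lower the SE only from 0.281 to 0.270 SD. This stands, and limits the claim.
- **Proportion.** There is no primary clinical outcome and no hypothesis test. That argues for a light change, but the precision gain comes from data already collected.

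**Conclusion.** The point holds as a cheap improvement to a stated method. Section 10.4 plans an unadjusted NDI difference, by implication on about 19 of 24 per arm, and no rule in the SAP reaches missing NDI questionnaires.

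The firmer gain is precision: the SE falls from about 0.32 to 0.28 SD even when loss is random, mostly from baseline adjustment. The protection against bias is conditional. If loss follows 14-week NDI in one arm only, the raw difference could plausibly shift by about 0.1 to 0.2 SD, enough to move the example reading in 10.4. A shift of 0.3 SD needs a 1.5 SD gap in one arm or 0.75 SD gaps in opposite directions.

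All sizes rest on the assumed correlations of 0.5, 0.5 and 0.7 and on assumed gaps between completers and dropouts; the SAP gives no figure for either. The documents do not support saying that dropout alone would create an effect, or that the plan has no other provision for missing data.

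**What to change.** - In 10.4, state that the NDI difference is at 6 months.
- Estimate it, with its one-sided 80% and 90% limits, from a linear mixed model for repeated measures on 14-week and 6-month NDI, with arm-by-time and baseline-NDI-by-time terms and an unstructured covariance. Include everyone randomised with at least one follow-up NDI, and show the raw difference beside it.
- Report 30% responders as n/N per arm with the number missing.
- Add an NDI row with N at each visit to the outcome table in Appendix C, and print N at each point of the mean plots.

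**Cost.** SAP wording and one model in SPSS, which 10.1 already names; no new data. **Downside.** The estimate assumes that data are missing at random given baseline and 14-week NDI, and it is no longer a simple subtraction. Where dropouts have no 14-week score, the bias reduction beyond baseline adjustment disappears.
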